### 2.3.2 Benefits

A direct benefit to this patient population will likely not be encountered during this study's duration. Benefits will be seen in future patient populations as the vascuCAP™ imaging technology will be better able to identify, categorize, and score problematic vascular beds.

### 2.3.3 Risk to Benefit Ratio

The risk to this patient population is considered minimal, while the potential benefit of progressing the vascuCAP™ noninvasive imaging technology could potentially allow for limited use of more invasive imaging techniques, such a angiography, in future patients. Accurate noninvasive plaque characteristics and risk scoring could also lead to individualized patient management based on predicted plaque stability through vascuCAP™ imaging. Future accurate

---

plaque assessment could potentially lead to noninvasive assessment of drug, example statins, influence on individual arterial lesions.

#### **2.3.4     *Therapeutic Alternatives***

Therapeutic alternatives would be limited as the MRI the patients would be set to undergo would be a part of their routine clinical workup. Although for select patients, alternative imaging strategies could include ultrasound, CT/CTA, and/or invasive angiography.

### 3 OBJECTIVES

#### 3.1 Study Objectives

The vascuCAP™ measurements of structural and functional features of the arterial wall will be performed in patients undergoing endarterectomy for the following objectives:

Primary:

- I. Measure the bias, precision, and reproducibility of each of the functional analytes as measured by vascuCAP™ with respect to histopathologic results as ground truth, and assess their linear region and limits of quantitation.
- II. Establish performance characteristics of the structural and hemodynamic analytes, where an objective truth standard is lacking.

Secondary:

- III. Classify the target lesion according to whether the analytes suggest it is not a plaque, or if it is, which of the 8 AHA types best fits the analyte profile. Assess the accuracy of vascuCAP™'s classification against the histopathology classification.

#### 3.2 Study Outcome Measures

Measured results will be compared in a blinded fashion with histology to assess performance of vascuCAP™-Profiling and build a prediction model in vascuCAP™-Scoring according to the following study endpoints:

- I. Measure the bias, precision, and reproducibility of each of the functional analytes as measured by vascuCAP™ with respect to histopathologic results as ground truth, and assess their linear region and limits of quantitation:
  - a. Plaque lipid core pool presence and volume.
  - b. Plaque fibrosis volume, degree, and uniformity.
  - c. Plaque inflammation burden, degree, and uniformity.
  - d. Intra-plaque hemorrhage burden and confidence.
  - e. Plaque vascular leak - volume, degree, and uniformity.
  - f. Calcification – volume, degree, and uniformity.
- II. Establish performance characteristics of the structural and hemodynamic analytes, where an objective truth standard is lacking:
  - a. Determine the interchangeability of structural measurements of wall thickness, remodeling ratio and luminal narrowing and hemodynamic measurements (ESS) with an imperfect (subjective) reference standard of manual contouring by radiologists. vascuCAP™ will be evaluated under two scenarios: fully-automated vascuCAP™, and a workflow where a reader will have the opportunity to review and adjust vascuCAP™ produced results.
  - b. Assess the reproducibility under different clinical sites, scanner models, and field strengths (dependent variable of interest being the interchangeability for each analyte relative to the imperfect reference standard) and with respect to ranges documented in literature according to collected co-variates.
- III. Classify the target lesion according to whether the analytes suggest it is not a plaque, or if it is, which of the 8 AHA types best fits the analyte profile. Assess the accuracy of vascuCAP™'s classification against the histopathology classification.

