### 8.1 Aim I

The first study aim is to estimate the bias and precision of each of the following functional analytes, which will be measured for each target lesion by both vascuCAP™ and histopathology:

- a. Plaque lipid
- b. Plaque fibrosis
- c. Plaque inflammation
- d. Intra-plaque hemorrhage burden and confidence.
- e. Plaque vascular leak
- f. Calcification

For each of these functional analytes, three measurements will be evaluated for a total of 18 measurements per target lesion: volume in mm^3, and degree and uniformity both measured on a three-point ordinal scale. The same measurements will be taken via histopathology, where the volume of each analyte will be measured using the same units (i.e. mm^3); however, degree and uniformity are graded subjectively on histopathology by the pathologist.

We anticipate that each patient will have at least one target lesion and some patients, especially the PAD patients, will have two target lesions, on average. There will be no replicate measurements (i.e. all of the measurements are obtained objectively by the algorithm so multiple runs should not produce different results).

For volume measurements for each analyte for each site (i.e. neck and leg), we will plot the value measured by histopathology vs. the difference between the value measured by vascuCAP™ and the value measured by histopathology. Any analyte not measurable will also be indicated on the plot using a different plotting character. The resulting plot will be inspected visually for the following:

1. Limits of vascuCAP™'s quantitation;
2. Associations between the magnitude of the histopathology measurement and bias; and
3. Associations between the magnitude of the histopathology measurements and heteroscedasticity in the vascuCAP™ measurements.

If the plots of carotid and femoral endarterectomies have similar distributions, then the data from these sites will be pooled; otherwise, separate analyses will be performed.

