A linear model will be fit (for all of the data or for a subset of histopathology values, depending on the findings from the plot) where the dependent variable is the vascuCAP™ measurement ( $X$ ) and the independent variable is the histopathology value ( $Y$ ). Generalized estimating equations (GEEs) (to account for the fact that some patients will have more than one target lesion) will be used to estimate the linear function:  $E(Y|X) = \beta_0 + \beta_1 X$ . An unstructured working covariance will be used. We will construct a 95% CI for the intercept  $\beta_0$  using a t-statistic as the pivotal statistic. CIs not containing 0 indicate fixed bias. We will also construct a 95% CI for the slope  $\beta_1$ . CIs not containing 1 indicate proportional bias [11].

The precision of the vascuCAP™ measurements will be estimated by the standard deviation:

$$\sqrt{\frac{1}{n-1} \sum_{i=1}^n (Y_i - X_i - \bar{d})^2} \text{ where } \bar{d} \text{ is the sample mean of the differences, } \bar{d} = \frac{1}{n} \sum_{i=1}^n (Y_i - X_i) \text{ [1].}$$

We will construct a 95% CI for the precision using bootstrap methods.

We will plot the bias profile (plot of bias of measurements for various ranges of histopathology values vs. the histopathology value) and precision profile (plot of standard deviation of vascuCAP™ measurements from patients with similar histopathology values vs. the histopathology value) as visual summaries of vascuCAP™ performance for the bias and precision components, respectively [12].

In addition to reporting these technical performance characteristics of the volume measurements, we will also report i) the coverage probability (CP) and ii) a discrimination index [11]. The CP is the probability that the absolute difference between the value measured by vascuCAP™ and the value measured by histology is less than  $d_0$ , i.e.  $\pi = \Pr(|Y - X| < d_0)$ . We will plot the CP for a range of values for  $d_0$ . The discrimination ability of the measurements, i.e. the ability of vascuCAP™ to discriminate between different magnitudes of histopathology values, will be measured using the area under the ROC curve for continuous measures [13]. 95% CIs for the CP and ROC area will be constructed using methods for clustered binary data [14] and clustered ROC data [15], respectively.

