The volume measurements are considered the most critical because they will be used to construct a score to predict rupture risk. Thus, we considered the width of 95% confidence intervals for the bias and the between-subject variance as a function of sample size (see Tables 1 and 2). The following assumptions were made: 1) the volume measurements are normally distributed; 2) carotid artery patients contribute one target lesion each, while PAD patients contribute two target lesions each; 3) target lesions from the same patient are moderately correlated ( $r=0.5$ ); 4) one-quarter of all patients will be PAD patients; 5) results from femoral and carotid target lesions can be pooled; 6) the average volume of an analyte is  $25\text{mm}^3$ ; and 6) the precision of the vascuCAP™ measurements is 10-20% of the volume of analyte.

From Table 4, if the SD was 15% of the mean volume, then we expect to be able to construct a 95% CI for the bias of total width of 10% with  $n=35$ . If the SD was 20%, then with  $n=35$  we expect to construct a 95% CI of total width of 14%. Similarly, from Table 5, if the SD was 15% of the mean volume, then with  $n=35$  we expect to be able to construct a 95% CI for the precision of total length 8%; if the SD was 20%, then we expect to be able to construct a 95% CI for the precision of total length 11%. We plan to recruit 75 patients (55 carotid artery patients and 20 PAD patients) in phase one to account for the fact that the estimates of bias and

precision may need to be reported in strata based on the magnitude of the histopathology volume and/or by anatomic location. In phase two we plan to recruit at least the minimum of 35 (25 carotid artery patients and 10 PAD patients) and possibly more depending on the results of the training set.

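### Limits of quantitation belong to primary objective I, but Section 8.1 finds them only by eye on a mm³ difference plot, so a lower limit could be missed and cannot be determined reproducibly

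*Combined protocol and SAP*

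**What the plan says.** Sections 3.1 and 3.2 put the task in primary objective I: for each functional analyte the study will "assess their linear region and limits of quantitation".

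For volumes, Section 8.1 gives the method: "we will plot the value measured by histopathology vs. the difference between the value measured by vascuCAP™ and the value measured by histopathology". It continues: "The resulting plot will be inspected visually for the following", and the limits of quantitation are the first item on the list. The third item is "Associations between the magnitude of the histopathology measurements and heteroscedasticity in the vascuCAP™ measurements", also judged by eye. For failures, "Any analyte not measurable will also be indicated on the plot using a different plotting character".

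The same plot decides the range of the linear model, which is fitted "for all of the data or for a subset of histopathology values, depending on the findings from the plot".

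Section 8.1 also has a precision profile, described as a "plot of standard deviation of vascuCAP™ measurements from patients with similar histopathology values vs. the histopathology value". It is offered as a visual summary, carries no threshold and is not linked to a limit of quantitation. Bias, precision, coverage probability and ROC area each receive a 95% confidence interval. The limit of quantitation receives none.

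**The concern.** A lower limit of quantitation is naturally read as the volume below which relative error is no longer acceptable. The plan never says what is acceptable, and it looks for the limit on an absolute scale. An error of 2.5 mm³ sits at the same height on the plot whether the lesion holds 5 mm³ (2.5/5 = 50%) or 25 mm³ (2.5/25 = 10%). Two competent readers could report different limits from the same plot, or none, and neither could be shown wrong.

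At stake is one component of a primary objective for six analytes. Under Section 4, the phase-two data are the definitive results for the 510(k) application. Section 8.1 calls the volume measurements the most critical ones. The same visual judgement also selects the data for the linear model, and so reaches the bias estimates.

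**Working it through.** **1. The plan's nearest figure.** The documents give no planning figure for a limit of quantitation. The closest is the interval for bias at n = 35. From the Table 4 footnote, m = (3/4)(35) + (1/4)(35)(2/1.5) = 26.25 + 11.67 = 37.9. With SD 3.75 mm³ the half-width is t × 3.75/√37.9 = 1.23 mm³, so the total width is 2 × 1.23/25 = 9.9%. The plan says 10%, so the figure reproduces. It describes average bias over all volumes and does not bear on where quantitation fails.

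**2. What each error structure looks like on the plot.** All three are scaled to SD 3.75 mm³ (15%) at the plan's mean of 25 mm³. The 2 mm³ floor is an assumption; its proportional part is b = √(0.15² − (2/25)²) = 0.127, and SD(V) = √(a² + (bV)²).

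| Volume (mm³) | Constant SD | Floor 2 mm³ + 12.7% | Proportional 15% |
|---|---|---|---|
| 5 | 3.75 (75%) | 2.10 (42%) | 0.75 (15%) |
| 10 | 3.75 (38%) | 2.37 (24%) | 1.50 (15%) |
| 25 | 3.75 (15%) | 3.75 (15%) | 3.75 (15%) |
| 50 | 3.75 (8%) | 6.65 (13%) | 7.50 (15%) |

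Under constant SD the plot is a flat band, although relative error rises fivefold between 25 and 5 mm³. Under a floor plus proportional error the band narrows just where relative error is worst. Under purely proportional error it also narrows, but precision then implies no lower limit. The second and third cases look alike to the eye and have different answers.

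**3. How much an unstated criterion moves the limit.** If relative SD of at most c is tolerated, the limit is a/√(c² − b²). For a 2 mm³ floor and c = 20%: 2/√(0.0400 − 0.0161) = 12.9 mm³.

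| Assumed floor (15% at 25 mm³) | c = 20% | c = 30% | c = 50% |
|---|---|---|---|
| 1 mm³ | 7.2 | 3.8 | 2.1 |
| 2 mm³ | 12.9 | 7.4 | 4.1 |
| 3 mm³ | 16.8 | 10.5 | 6.1 |

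**4. A simulated phase two.** The minimum phase two has 25 carotid + 2 × 10 PAD = 45 lesions, treated here as independent. Assumed: lognormal volumes with mean 25 mm³ and CV 80%, a = 2.5 mm³, b = 0.10.

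- The limit at 20% relative SD is 2.5/√(0.04 − 0.01) = 14.4 mm³, with 33% of lesions below it (24% to 40% for volume CVs of 60% to 100%). With a 1.25 mm³ floor the limit is 7.2 mm³, with 8% below.
- In 98% of runs the smallest third of lesions scatters less in mm³ than the largest third (mean SD 2.7 against 5.4), although its relative error is 33% against 12%. It is the least scattered of all three thirds in 71% of runs.
- With constant SD 3.75 mm³, the smallest third scatters less than the largest in about half of runs (49%), so the plot is flat, while relative error is 47% against 10%.

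**5. Whether the limit can be estimated.** Fitting SD(V)² = a² + (bV)² to 45 lesions under the same assumptions gives a median limit of 14.1 mm³, with a 95% sampling range of 8.5 to 18.9. This is a favourable test, because the fitted model also generated the data. With b = 0.15, about 6% of fits give no finite limit at c = 20%; with b = 0.20, about half do. At b = 0.20 the formula itself has no solution.

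**The case against.** The plan is not blind to the problem. The horizontal axis is histology volume, so a careful reader can work out relative error. Unmeasurable results are marked, heteroscedasticity is inspected, and dividing the precision profile by volume gives a CV. Phase one (75 patients, 55 + 2 × 20 = 95 lesions under the plan's assumptions) is analysed before the product is locked, so a criterion could still be set in time. All of this stands, and it limits the point. It does not supply a criterion, an estimate or an interval. The symbol shows where no value was returned, not where a value was returned with unacceptable error. Coverage probability uses an absolute d₀ and is not broken down by volume.

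A reader might infer three stronger things that the documents do not support:

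- *Small volumes always scatter least, so a limit would be missed.* This depends on the error structure. It fails under constant SD, which Tables 4 and 5 use, and under purely proportional error precision sets no lower limit. Nothing here tests what a human reader would actually see.
- *The plan has already set 20% as its limit.* The statement that "the precision of the vascuCAP™ measurements is 10-20% of the volume of analyte" is one of the sample-size assumptions, not an acceptance limit.
- *Volumes below the limit will pass unflagged into the risk score.* Section 8.1 says that volumes will feed a score, but nothing in the documents says how readings below a limit would be handled.

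**Conclusion.** The point holds in a limited form. A component of primary objective I has no numerical definition, estimator or interval, and its only stated method uses a scale on which poor relative precision at small volumes may not show. A lower limit could be missed, and it cannot be determined reproducibly. That does not depend on any simulation.

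The size does depend on assumptions. The range of about 2 to 17 mm³ rests on assumed floors of 1 to 3 mm³ and tolerances of 20% to 50%. The 14.4 mm³ and 33% figures are illustrations under one assumed error model and volume distribution, not predictions for vascuCAP. The bias, precision and coverage analyses remain usable as planned, apart from the plot-based choice of range for the linear fit. This is an inexpensive improvement to make before phase two.

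**What to change.** In Section 8.1:

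1. Add a plot of relative differences and a CV version of the precision profile, over non-zero histology volumes. Handle zero volumes separately, since relative error is undefined there.
2. Define the lower limit of quantitation as the smallest histology volume above which both relative SD and relative bias stay within a limit that the sponsor states and justifies from phase-one data, before phase-two results are seen.
3. Estimate it for each analyte from a fitted variance function, for example SD(V)² = a² + (bV)², together with the fitted bias, and give a patient-level bootstrap 95% confidence interval.
4. State that, when there is no finite solution, the report will say that no limit was met within the observed range.
5. Note that the differences include histology error as well as vascuCAP error, so the limit describes the comparison and not the software alone.

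The cost is SAP wording and a little programming, with no new data. The drawbacks are a possibly less favourable reported limit and, at 45 lesions, wide or non-estimable intervals for some analytes.

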#### 4 STUDY DESIGN

A two-phase study is proposed. In the first phase, 75 surgical patients will be recruited as part of a training set; aims I-II will be evaluated with this set. In the second phase, at least a minimum of 35 and as many as 75 surgical patients will be recruited (number to be set based on the results of a statistical analysis following the first phase). Data from the second phase will be used in the definitive results to be filed in a 510(k) application to the FDA documenting the statistical performance of vascuCAP™'s ability to measure functional and structural analytes according to Aims I and II. Data collected in the second phase will also be used as additional training data for Aim III.

vascuCAP™'s performance in measuring functional analytes will be assessed using histology of specimens collected during surgery as ground truth. vascuCAP™'s performance in measuring structural analytes will be facilitated by comparing its automated segmentations against manual contours produced independently by two radiologists recruited for the study. The two radiologists will independently perform the manual contouring for all study patients, and one of these two radiologists will also perform the vascuCAP™ aided contouring after a sufficient wash-out period after the manual contouring and with appropriate blinding to their manual results.

Patients are recruited, enrolled, and analyzed with vascuCAP™. 75 patients which have been imaged and on which surgery was performed within 30 days of imaging will form the training set. An analysis will be performed and revisions to vascuCAP™ will be made, as appropriate. The sample size for the *Profiling* will be determined at this time; we denote this as  $N_{\text{profile}}$ . After analysis, the product configuration will be locked, and subsequent patient results are blinded. After  $N_{\text{profile}}$  additional patients have been imaged and on which surgery was performed within 30 days of imaging ( $N_{\text{profile}} \geq 35$ ).

## 5 STUDY ENROLLMENT AND WITHDRAWAL

Patients scheduled for MRA and endarterectomy at the LSU ILH Medical Center, New Orleans as well as West Jefferson Medical Center, Marrero will be recruited for the study after informed consent has been obtained. All patients will undergo a carotid or femoral artery MRI examination within 30 days of the surgical procedure. Patients will not be coerced into enrolling within the study. Patients will be reminded of their freedom to abstain from enrollment. Patients will be reminded that upon abstaining from enrollment, no objective or subjective change will/would occur in their care.

### Current Standard of Care and Deviation Thereof:

Patients will be recruited, enrolled, and the vascular bed in question analyzed with MRI and the vascuCAP™ system. For a patient to be included within the appropriate phases as described previously, any vascular operation upon the vascular bed in question must take place within 30 days of the vascuCAP™ study. MRI for carotid and femoral arterial atherosclerotic lesions is consistent with current standard of care [7]. Carotid and femoral lesion vessel distribution and percent stenosis can be accurately assessed with MRI. Thus, preoperative imagining via MRI is sufficient to construct an appropriate operative plan for individual patients. The MRI which will be required for patients to undergo will *not* be an addition to their clinical work up had they not enrolled in the study. Therefore, no additional risk will be seen by patients outside of the standard clinical workup for their specific disease.

### 5.1 Subject Inclusion Criteria

Individuals must meet one of the following inclusion criteria in order to be eligible to participate in the study:

- a. Case subjects will be patients with documented carotid atherosclerosis, scheduled for magnetic resonance angiography and subsequent elective endarterectomy with 30 days of enrollment in the study
- b. Case subjects will be patients with peripheral arterial disease (PAD) with clinical symptoms, scheduled for magnetic resonance angiography and indicated endarterectomy of diseased areas of femoral arteries within 30 days of enrollment in the study

### 5.2 Subject Exclusion Criteria

Individual meeting any of the following criteria will be excluded from participation in this study:

- a. Subjects with claustrophobia or inability to tolerate prior MRI studies.
- b. Subjects with metal implants that are not MRI compatible (LSU detailed checklist to be attached) including: Subjects with any type of bio-implant activated by mechanical, electronic, or magnetic means (e.g. cochlear implants, pacemakers, neurostimulators, biostimulators, electronic infusion pumps, etc.). Subjects with any type of ferromagnetic bio-implant that could potentially be displaced or damaged, such as aneurysm clips, metallic skull plates, etc.
- c. Subjects with a history of kidney disease or dialysis that are unable to receive intravenous gadolinium contrast material.
- d. Female subjects. A urine pregnancy test will be required of all female subjects of

childbearing potential prior to inclusion in this study. Pregnant or nursing females will be excluded from the study.

- e. Subjects who cannot adhere to the experimental protocol.
- f. Subjects allergic to gadolinium contrast material.

